### **6.14 Treatments to be Used with Caution**

Medications that are potent substrates, inhibitors or inducers of P450 cytochromes, in particular CYP3A4 (see [Appendix C](#)), should be avoided when possible but are not prohibited.

Medications that prolong the QTcB interval should be avoided when possible but are not prohibited. If such medications are deemed necessary and used while a participant is on study, additional ECG monitoring should be performed as clinically indicated.

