#### **AP24534-11-103**

Trial AP24534-11-103 investigated potential drug-drug interactions of ponatinib. The objective of this study was to determine the effects of concomitant ketoconazole administration on the pharmacokinetic profile of single-dose ponatinib in 22 healthy subjects. Ketoconazole is a strong inhibitor of CYP3A4. This study demonstrated a statistically significant effect of ketoconazole co-administration on the relative bioavailability of ponatinib along with its

CYP3A4/5 metabolite, AP24567. Specifically, ketoconazole co-administration increased the  $C_{max}$  and AUC of ponatinib by 47% and 78%, respectively.

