Clinically, RET has served as a therapeutic target in the treatment of other malignancies, such as medullary thyroid cancer (Wells et al, 2010). Germline mutations in RET underlie multiple endocrine neoplasia type 2 (MEN 2) and familial medullary thyroid carcinoma, while somatic mutations in RET are seen in approximately 50% of sporadic medullary thyroid carcinomas (Romei et al, 1996; Marsh et al, 1996). Given the central oncogenic role of RET in medullary thyroid carcinoma, recent efforts have focused on targeting this oncogene through targeted tyrosine kinase inhibition. Vandetanib is an oral TKI that selectively targets RET, vascular endothelial growth factor (VEGF), and EGFR. In a phase III randomized trial in patients with locally advanced or metastatic medullary thyroid carcinoma, vandetanib resulted in improved response rates and progression-free survival compared to placebo, suggesting that RET can be a viable novel target (Wells et al, 2010).

In this phase II, open label study, we propose use of the orally available TKI ponatinib in the treatment of patients with NSCLC harboring translocations in RET. Ponatinib has broad activity against a range of tyrosine kinases, including extremely potent inhibition of RET. In vitro, ponatinib inhibits RET kinase activity with an  $IC_{50}$  of 0.16 nM ([Ponatinib Clinical Investigator's Brochure, 10Apr2012](#)). Given its favorable toxicity profile and potent RET inhibition, there is strong rationale for the use of ponatinib in this molecularly-defined subpopulation of patients with NSCLC.

Participants will receive ponatinib at a dose of 30 mg orally once daily, which is below the maximum tolerated dose (45 mg once daily). This is based upon available pharmacokinetic, safety, and efficacy data from CML patients treated with ponatinib. In prior studies of ponatinib in the CML population, rates of adverse events (e.g. thrombocytopenia, neutropenia, rash, ALT/AST elevation, pancreatitis, and lipase elevation) appeared to correlate with increasing doses of ponatinib

([http://www.accessdata.fda.gov/drugsatfda\\_docs/nda/2012/203469Orig1s000ClinPharmR.pdf](http://www.accessdata.fda.gov/drugsatfda_docs/nda/2012/203469Orig1s000ClinPharmR.pdf) Accessed 10/13/2013). In addition, larger doses of ponatinib were associated with higher grades of ischemia

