### **6.15 Potential Drug-Drug Interactions**

In vitro and in vivo studies have demonstrated that CYP3A4 is involved in the metabolism of ponatinib. Therefore, drug-drug interactions (DDIs) are possible if ponatinib is given with substrates, inhibitors or inducers of CYP3A4 (see [Appendix C](#)). Investigators are encouraged to avoid administration of drugs that are substrates, inhibitors or inducers of CYP3A4 if clinically feasible.

Additionally, medications associated with prolongation of the QTc interval may interact with ponatinib and contribute to further QTc prolongation, which has the potential to contribute to ventricular arrhythmia. In addition, some medications associated with QTc prolongation also interact with the CYP3A4 cytochrome and an effect on the QTc interval might thus be exacerbated.

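### Strong CYP3A4 inhibitors are discouraged but still permitted, with no ponatinib dose rule when one is unavoidable and no co-medication check for 45 mg

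*Combined protocol and SAP*

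**What the plan says.** Section 6.14 covers "Medications that are potent substrates, inhibitors or inducers of P450 cytochromes, in particular CYP3A4" and says that they "should be avoided when possible but are not prohibited". Section 6.15 adds: "Investigators are encouraged to avoid administration of drugs that are substrates, inhibitors or inducers of CYP3A4 if clinically feasible". Appendix C lists drugs to be used with caution, says the list is not complete, and sends questions to the medical monitor.

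Some drugs are barred on other grounds. Section 6.13, with Appendix B and exclusion 3.2.15, prohibits Torsades drugs, clarithromycin among them. Section 6.13 also bars other anti-cancer agents and herbal preparations.

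Section 6.14 treats its second class, drugs that prolong QTcB, differently. It gives a fallback for when they are needed: "If such medications are deemed necessary and used while a participant is on study, additional ECG monitoring should be performed as clinically indicated".

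On the interaction itself, the account of study AP24534-11-103 in section 2.1 says "Ketoconazole is a strong inhibitor of CYP3A4" and reports that giving it with ponatinib increased the Cmax "and AUC of ponatinib by 47% and 78%, respectively".

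Dose changes are set out in three places:

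- Table 7.1 lists responses to study-drug toxicity.
- Section 7.3 calls that table suggested guidance, lets the investigator also weigh the clinical circumstance, sets a floor of 15 mg, and bars re-escalation once a dose has been reduced.
- Section 7.4 allows 45 mg if there has been no vascular toxicity, no grade 3/4 treatment-related toxicity, and the sponsor approves.

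**The concern.** Sections 6.14 and 6.15 both foresee that a CYP3A4 inhibitor may sometimes be unavoidable, and both stop there. The investigator then has an interaction figure in the background section but no stated dose to give. Nor does section 7.4 ask about inhibitors before escalation, or say what to do if one is started after a participant has reached 45 mg.

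What is at stake is the safety margin. Section 2.3 explains that 30 mg was chosen to lower the risk of adverse events, noting that "larger doses of ponatinib were associated with higher grades of ischemia". A strong inhibitor at an unchanged dose could use up that margin. A rule that waits for toxicity may suit a lipase rise. It suits vascular occlusion less well: section 2.1 says these events can be fatal, have occurred within two weeks of starting, and have occurred at doses as low as 15 mg per day. Scheduled PK sampling (Cycle 1 Day 1 and Cycle 2 Day 1) would not detect raised exposure from an inhibitor started later.

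**Working it through.** The plan gives no figure of its own for ponatinib exposure with an inhibitor, so there is none to reproduce. The inputs are:

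- AUC ratio 1.78 and Cmax ratio 1.47 with ketoconazole (section 2.1, AP24534-11-103)
- starting dose 30 mg, and 45 mg stated as the maximum tolerated dose (section 2.3)
- 60 mg as the level at which four patients had pancreatic dose-limiting toxicities (section 2.1, AP24534-07-101)
- minimum dose 15 mg (section 7.3), supplied as a 15 mg tablet (section 6.4)

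**Base case.** Two assumptions are needed, and the documents state neither: the single-dose healthy-subject ratio carries over to these patients, and exposure is proportional to dose. Then equivalent dose = dose × ratio.

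| Ponatinib dose | AUC-equivalent (× 1.78) | Cmax-equivalent (× 1.47) |
|---|---|---|
| 15 mg | 26.7 mg | 22.1 mg |
| 30 mg | 53.4 mg | 44.1 mg |
| 45 mg | 80.1 mg | 66.2 mg |

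- 30 mg by AUC: 53.4/45 = 119% of the stated maximum tolerated dose, and 53.4/60 = 89% of the 60 mg level.
- 30 mg by Cmax: 44.1/45 = 98%, just under the maximum tolerated dose.
- 45 mg: 80.1/60 = 134% by AUC and 66.15/60 = 110% by Cmax.
- 15 mg by AUC: 26.7/30 = 89% of the starting dose without an inhibitor. The dose that would match 30 mg exactly is 30/1.78 = 16.9 mg, so the 15 mg tablet is close.

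**If AUC is not proportional to dose.** Let AUC rise as dose to the power b. Then equivalent dose = dose × 1.78^(1/b).

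| b | 15 mg | 30 mg | 45 mg |
|---|---|---|---|
| 0.8 | 30.8 | 61.7 | 92.5 |
| 1.0 | 26.7 | 53.4 | 80.1 |
| 1.2 | 24.3 | 48.5 | 72.8 |

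Break-even exponents:

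- 30 mg passes 45 mg if b < ln 1.78 / ln 1.5 = 1.42.
- 30 mg passes 60 mg only if b < ln 1.78 / ln 2 = 0.83.
- 45 mg passes 60 mg if b < ln 1.78 / ln(60/45) = 2.00.
- 15 mg stays below 45 mg if b > ln 1.78 / ln 3 = 0.52.

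**If the inhibitor is weaker.** At an assumed AUC ratio of 1.25, 30 mg gives 37.5 mg and 45 mg gives 56.3 mg, so neither line is crossed. A reduction to 15 mg would then give 18.8 mg, or 18.75/30 = 63% of the starting exposure.

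**The case against.** The best defence is that avoid-if-possible is a deliberate choice backed by several safeguards. Concomitant medications are recorded throughout treatment. Chemistry, including amylase and lipase, is drawn at Cycle 1 Days 1 and 15, Cycle 2 Days 1 and 15, and every four weeks in cycles 3 to 10. Table 7.1 has hold rules, the medical monitor takes questions, and 45 mg needs sponsor approval case by case. On the base-case figures, 30 mg with ketoconazole stays below 60 mg by AUC and below 45 mg by Cmax. The 80 mg figure requires both escalation and a strong inhibitor used against advice. Most of this stands and keeps the point small. But none of these safeguards is a dose rule set in advance, and sponsor approval at escalation would not catch an inhibitor started afterwards.

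A reader might go further than the documents allow in five ways.

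- That dose may change only for toxicity. Section 7.3 also refers to the clinical circumstance and clinical judgment, so a precautionary reduction is open to the investigator; it is just not specified.
- That investigators had no interaction dosing guidance. The protocol relies on an Investigator's Brochure and a package insert that were not available for this review, and either may supply it.
- That particular Appendix C drugs, such as the azole antifungals, are strong inhibitors. The appendix does not label direction or potency, and only ketoconazole is called strong.
- That the gap contradicts section 2.3. That section sets a nominal starting dose and itself allows 45 mg.
- That the efficacy analysis is compromised. Nothing here changes the rule of at least 4 responses in 20 or its stated error rates.

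**Conclusion.** The point holds as a gap in the visible protocol text. Strong CYP3A4 inhibitors not barred by section 6.13 remain allowed, no section sets a ponatinib dose to go with them, and section 7.4 does not consider them before or during 45 mg. On the protocol's own ketoconazole ratio, a participant treated as written could have exposure above that of the 45 mg maximum tolerated dose while taking 30 mg (by AUC only), or above that of the 60 mg level while taking 45 mg (by AUC and Cmax).

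This rests on the single-dose ratio carrying over and on dose-proportionality. The AUC crossings survive moderate departures from proportionality but disappear at an inhibitor ratio of 1.25. How many participants would be exposed is unknown. Severity is minor: a cheap safety improvement with no bearing on the primary analysis.

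**What to change.** Three short additions:

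1. **Sections 6.14 and 6.15.** If a strong CYP3A4 inhibitor (ketoconazole-strength, confirmed with the medical monitor if unclear) cannot be avoided, reduce ponatinib to 15 mg while it is taken. For a participant already at 15 mg, the section 7.3 floor, the Principal Investigator/Sponsor joins the decision to hold or continue. An automatic hold is not clearly better, because 26.7 mg-equivalent is still below the 30 mg starting dose and a hold interrupts cancer treatment.
2. **Section 7.4.** Add the absence of a concurrent strong CYP3A4 inhibitor as a condition for starting and for staying on 45 mg.
3. **Section 7.3.** State that this temporary precautionary reduction is exempt from the ban on re-escalation. That sentence sits in a section about adverse events but is worded broadly enough to make the reduction permanent.

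A precautionary interruption is not new to this protocol: section 6.12 already requires ponatinib to be held around radiation.

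The costs are some lost exposure if the inhibitor is weaker than ketoconazole (18.8 mg-equivalent at a ratio of 1.25) and a routine amendment. Section 12.1 requires IRB approval before implementation, and Appendix D gives participating sites up to 90 days. No new data are collected, and the sample size and decision rule do not change. The additions cover inhibitors only; inducers, which section 6.14 also names, would need separate thought.

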### **6.15 Potential Drug-Drug Interactions**

In vitro and in vivo studies have demonstrated that CYP3A4 is involved in the metabolism of ponatinib. Therefore, drug-drug interactions (DDIs) are possible if ponatinib is given with substrates, inhibitors or inducers of CYP3A4 (see [Appendix C](#)). Investigators are encouraged to avoid administration of drugs that are substrates, inhibitors or inducers of CYP3A4 if clinically feasible.

Additionally, medications associated with prolongation of the QTc interval may interact with ponatinib and contribute to further QTc prolongation, which has the potential to contribute to ventricular arrhythmia. In addition, some medications associated with QTc prolongation also interact with the CYP3A4 cytochrome and an effect on the QTc interval might thus be exacerbated.

## **7 Expected Toxicities and Dose Modifications**

The most common expected toxicities for ponatinib include rash, dry skin, thrombocytopenia, abdominal pain, elevations in amylase and lipase, pancreatitis, anemia, neutropenia, hypertension, QTc prolongation, hepatotoxicity, headache, fatigue and myalgias. Please see [Table 2.2](#) for the frequencies of adverse events in the previous ponatinib phase II trial AP24534-10-201. For dose modifications and toxicity-specific management, please refer to [Table 7.1](#) and [Section 7.5](#).

## **7.1 Management of Adverse Drug Reactions**

Comprehensive assessments of any study drug-related adverse events experienced by the participant will be performed throughout the course of the study. The severity of the event, as well as clinical judgment, will be utilized to determine appropriate management of the participant for any AE experienced while participating in this trial.

## **7.2 Dose Delays and Reductions**

Dose delays and/or reductions will be implemented for participants who experience adverse drug reactions as indicated in the following sections.

### **7.3 Dose Delay and/or Reduction for Adverse Events (AEs) Attributable to the Study Drug**

[Table 7.1](#) describes suggested guidelines for dose modification due to study-drug-related toxicity, graded according to NCI CTCAE 4.0. However, for an individual participant, dose interruptions, reductions and treatment discontinuation should also be based on the clinical circumstance and investigators should use clinical judgment in deciding whether a dose reduction, delay or discontinuation is appropriate for any given clinical circumstance. In general, when the observed toxicity has resolved to  $\leq$  grade 1, the investigator may resume full dosing if clinically indicated.

No dose reduction below 15 mg once daily is permitted for ponatinib. If the participant cannot tolerate a minimum dose of 15 mg per day of ponatinib, despite any allowed interruptions, the participant must be discontinued from study treatment. Doses may be interrupted for study-drug related toxicities for up to 28 days. If a non-hematologic study-drug related toxicity does not resolve to Grade 1 or less after dose interruption for more than 28 days, the participant must be discontinued from study treatment. If a hematologic study-drug related toxicity does not resolve to Grade 1 or less after dose interruption for more than 28 days, the Principal Investigator/Sponsor must be contacted. Additionally, the Principal Investigator/Sponsor must be contacted if any adverse event deemed unrelated to treatment requires dose interruption for more than 28 days. Lastly, for each participant, once a dose reduction has occurred, the dose level may not be re-escalated during subsequent treatment cycles of ponatinib.

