**Table 7.1 Ponatinib: Dose Modifications for Drug Adverse Reactions**

Toxicity	Modification
Nonhematologic Toxicity	
General (Any CTCAE v4.0 nonhematologic toxicity not otherwise specified below)	
Grade 1 or transient Grade 2	No intervention
AST/ALT Elevations	
Grade 1 or transient Grade 2	No intervention
Grade 2 lasting $\geq$ 7 days with optimal care AND total bilirubin $<$ 2 x ULN	Hold ponatinib Resume at 30 mg after recovery to $\leq$ grade 1  Recurrence at 30 mg: Hold ponatinib Resume at 15 mg after recovery to $\leq$ grade 1  Recurrence at 15 mg Discontinue ponatinib
Grade 3 or 4 AND total bilirubin $<$ 2 x ULN	Hold ponatinib Resume at 30 mg after recovery to $\leq$ grade 1  Recurrence at 30 mg Hold ponatinib Resume at 15 mg after recovery to $\leq$ grade 1  Recurrence at 15 mg Discontinue ponatinib
Grade $\geq$ 2 AND total bilirubin $\geq$ 2 x ULN (In the absence of liver metastases)	Discontinue ponatinib
Pancreatitis	
Grade 2 (enzyme elevation or radiologic findings only)	See amylase/lipase section below
Grade 3 (severe pain, vomiting, medical intervention indicated [eg, analgesia, nutritional support])	Hold ponatinib Perform ultrasound or abdominal CT scan with contrast If imaging is positive, continue holding ponatinib and repeat according to clinical care. If imaging is negative, or after resolution by imaging, resume at 15 mg after recovery to $\leq$ grade 1  Recurrence at 15 mg: Repeat above Consider discontinuing ponatinib
Grade 4	Hold ponatinib Consult sponsor
Amylase/Lipase	
Grade $\leq$ 2	No intervention; monitor closely

Toxicity	Modification
Grade 3 with no radiologic findings	Hold ponatinib Resume at 30 mg after recovery to $\leq$ grade 1  Recurrence at 30 mg: Hold ponatinib Resume at 15 mg after recovery to $\leq$ grade 1  Recurrence at 15 mg: Discontinue ponatinib
Grade 3 with radiologic findings or Grade 4	Hold ponatinib Repeat imaging according to clinical care After resolution by imaging, resume at 15 mg after recovery to $\leq$ grade 1  Recurrence at 15 mg: Discontinue ponatinib
LV dysfunction/CHF	
Grade 2 or 3	Hold ponatinib Resume at 30 mg after recovery to $\leq$ grade 1  Recurrence at 30 mg: Hold ponatinib Resume at 15 mg after recovery to $\leq$ grade 1  Recurrence at 15 mg: Discontinue ponatinib
Grade 4	Discontinue ponatinib
Skin rash	

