Grade 2 persistent despite optimal symptomatic therapy	Hold ponatinib Resume at 30 mg after recovery to $\leq$ grade 1  Recurrence at 30 mg: Hold ponatinib Resume at 15 mg after recovery to $\leq$ grade 1  Recurrence at 15 mg: Discontinue ponatinib
Grade 3 persistent despite optimal symptomatic therapy	Hold ponatinib Resume at 30 mg after recovery to $\leq$ grade 1  Recurrence at 30 mg: Hold ponatinib Resume at 15 mg after recovery to $\leq$ grade 1  Recurrence at 15 mg: Discontinue ponatinib

Toxicity	Modification
Hematologic Toxicity	
Drug-Related ANC/platelets	
Grade 1 or 2	No dose adjustment
Grade 3 or 4	Hold ponatinib Resume at 30 mg after recovery to $\leq$ grade 1  Recurrence at 30 mg: Hold ponatinib Resume at 15 mg after recovery to $\leq$ grade 1  Recurrence at 15 mg: Discontinue ponatinib

Definitions: ANC = absolute neutrophil count; CHF = congestive heart failure; CT = computed tomography; LV = left ventricular.

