## **7.4 Dose Escalation**

Participants who do not experience an objective response within 2-4 cycles of starting treatment with ponatinib may be candidates for dose-escalation of ponatinib to a dose of 45 mg once daily, provided the following criteria are met: 1) the participant has not experienced any vascular toxicities of any grade, 2) the participant has not experienced any grade 3/4 treatment-related toxicities, and 3) the treating investigator receives approval from the study Sponsor.

In addition, participants who achieve an objective response to therapy but subsequently relapse may also be candidates for dose escalation to a ponatinib dose of 45 mg once daily, provided the same criteria above are met.

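### Seven Table 7.1 rows restart ponatinib at 30 mg whatever the dose before the hold; for a participant already reduced to 15 mg, this conflicts with the Section 7.3 bar on re-escalation

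*Combined protocol and SAP*

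**What the plan says.** The starting dose is 30 mg daily (Section 6.2) and the floor is 15 mg daily (Section 7.3).

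Section 7.3 says that Table 7.1 "describes suggested guidelines for dose modification due to study-drug-related toxicity" and leaves interruption, reduction and discontinuation to clinical judgment. It adds that, in general, once toxicity has settled to grade 1 or less, "the investigator may resume full dosing if clinically indicated". It closes with a rule that applies per participant, not per toxicity: "once a dose reduction has occurred, the dose level may not be re-escalated during subsequent treatment cycles of ponatinib".

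In Table 7.1, seven rows begin with a hold and then "Resume at 30 mg after recovery to" grade 1 or less:

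- AST/ALT grade 2 lasting 7 days or more (bilirubin below 2 x ULN)
- AST/ALT grade 3 or 4 (bilirubin below 2 x ULN)
- amylase/lipase grade 3 without radiologic findings
- LV dysfunction/CHF grade 2 or 3
- rash, "Grade 2 persistent despite optimal symptomatic therapy"
- rash grade 3, likewise persistent
- ANC/platelets grade 3 or 4

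In these rows 15 mg appears only as the step after a recurrence at 30 mg.

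Two other rows go straight to 15 mg. For grade 3 pancreatitis the text is "If imaging is negative, or after resolution by imaging, resume at 15 mg after recovery to" grade 1 or less. The second is amylase/lipase grade 3 with radiologic findings, or grade 4. Grade 4 pancreatitis is handled separately: "Hold ponatinib Consult sponsor".

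**The concern.** The table gives no instruction for a first occurrence of a new toxicity in someone already at 15 mg. Read literally, the row for the new toxicity sends that person back to 30 mg, while Section 7.3 forbids it.

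What is at stake is participant safety. The dose rationale in Section 2.3 says that adverse events including pancreatitis, lipase elevation, thrombocytopenia and neutropenia appeared to rise with dose, that larger doses went with higher grades of ischemia, and that 30 mg was chosen to lower the risk. Doubling the dose after a toxicity-driven reduction works against that reasoning. The step also has no gate. Escalation to 45 mg under Section 7.4 requires no prior grade 3/4 treatment-related toxicity, no vascular toxicity and Sponsor approval; the 15 to 30 mg step in the table requires none of these.

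**Working it through.** The plan states no figure on this point, so the main check is a comparison of texts.

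**Step 1. Apply the restart instruction to each possible dose before the hold.** The possible doses are 45 mg (Section 7.4), 30 mg (Section 6.2) and 15 mg (Section 7.3 floor).

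| Dose before hold | Restart under the seven rows | Change | Against Section 7.3 |
|---|---|---|---|
| 45 mg | 30 mg | reduction | consistent |
| 30 mg | 30 mg | none | consistent |
| 15 mg | 30 mg | 30/15 = 2 times | barred |

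The result is the same in all seven rows (AST/ALT 2 + amylase/lipase 1 + LV dysfunction 1 + rash 2 + ANC/platelets 1 = 7).

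**Step 2. Can a participant reach 15 mg before a first event in one of these rows?** Yes. One grade 3 pancreatitis event leads directly to 15 mg. A later first grade 3 or 4 platelet event then falls under the ANC/platelets row, which says 30 mg. A recurrence at 30 mg in any of the seven rows is another way to reach 15 mg. Sections 7.5.2 and 7.5.4 place the usual onset of both myelosuppression and pancreatic events in the first month, and Section 7.5.4 expects almost all patients to continue treatment after a pancreatic event. The sequence is therefore plausible.

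**Step 3. Size, for the pancreatitis route only.** The inputs are 20 participants (Section 13.1) and treatment-related grade 3/4 pancreatitis in 21 of 449 (Table 2.2, 4.7%).

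- Expected participants with grade 3/4 pancreatitis: 20 x 21/449 = 0.94.
- Share who later have a first event in one of the seven rows: not in the documents; assumed 10% to 50%.
- Participants meeting the conflict: 0.94 x 0.10 = 0.09 to 0.94 x 0.50 = 0.47.
- At half the pancreatitis rate (assumption, for the lower dose): 0.47 x 0.10 = 0.05 to 0.47 x 0.50 = 0.23.

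The 0.94 overstates this route. It includes grade 4 events, which go to the Sponsor, and it comes from leukemia patients treated at 45 mg. The trial also excludes recent acute or any chronic pancreatitis (3.2.7) and requires lipase and amylase at or below 1.5 x ULN (3.1.13).

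The other routes to 15 mg cannot be sized. Table 2.2 reports grade 3/4 lipase increase in 35 of 449, but does not split it by grade or radiologic findings, and no recurrence rates at 30 mg are given.

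**Step 4. Test the proposed wording** (30 mg, or the last dose before the hold if lower). From 45 mg it gives 30 mg, from 30 mg it gives 30 mg, and from 15 mg it gives 15 mg. The existing line for a recurrence at 15 mg (discontinue) then follows without change.

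**The case against.** The strongest reply is that Section 7.3 already settles the matter. The table is only suggested guidance, the bar is categorical and per participant, and the rows read naturally as a ladder down from the 30 mg start: 30, then 15, then stop. Other text points the same way. Section 7.5.2 answers treatment-related cytopenias with a reduction or an interruption, Section 7.5.7 does the same for hepatotoxicity, and Section 7.5.4 speaks of continuing at an unchanged or lower dose.

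All of this stands as to which rule controls. It does not repair the rows. The opening of Section 7 and Sections 7.5.2 and 7.5.7 send staff to Table 7.1 without mentioning the bar, so working from the row alone is foreseeable. Being only a suggestion does not make a row acceptable when what it suggests is prohibited.

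Three stronger readings are tempting, and the documents do not support them.

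- *That Section 7.3 leaves re-escalation open.* A reader might point to "the investigator may resume full dosing if clinically indicated", or to the bar being worded for later cycles. The first is a general, discretionary statement that precedes the bar. The second would matter only if two toxicities, two holds and two recoveries fell within one 28-day cycle, and if the bar did not reach that case there would be no conflict in it.
- *That restarting at 30 mg, or going from 30 to 45 mg, itself breaks the rule.* A restart at 30 mg after a hold at 30 mg is the same dose, and a first escalation without a prior reduction is not a re-escalation.
- *That Section 7.4 is a second way around the bar.* Its criteria do not name a prior reduction, and the relapse paragraph applies "provided the same criteria above are met". But anyone with a grade 3/4 treatment-related toxicity or any vascular toxicity is already excluded, Sponsor approval is required, and the Section 7.3 bar still applies. Of the Table 7.1 routes to 15 mg, only grade 2 events would pass the toxicity criteria. No change to Section 7.4 is needed.

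**Conclusion.** The concern holds in a limited form. A participant at 15 mg with a first new toxicity in one of seven rows gets two incompatible instructions, and the one in the table doubles the dose. Section 7.3 controls and is correct; the rows are wrong for this case only.

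The reach is small, likely well under one participant of 20. That is a judgment. The 0.05 to 0.47 range covers the pancreatitis route alone and rests on an assumed share of later events and a rate borrowed from another population and dose. An actual re-escalation would further require a site to follow the row and overlook Section 7.3.

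This is a low-frequency safety correction. The decision rule (at least 4 responses in 20, with rates of 10% and 30%) does not depend on these rows, so sample size, power and type I error do not change. The case for acting rests on participant safety and the very low cost of the repair.

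**What to change.** In each of the seven rows, or in one footnote to Table 7.1 that covers them, write: *Resume at 30 mg, or at the last dose taken before the hold if lower (no re-escalation after a dose reduction; see Section 7.3).* Referring to the last dose before the hold is clearer than referring to the current dose, because no drug is being taken during a hold.

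The change adds no new dose and no new policy; it makes the rows match Section 7.3. The cost is one footnote, or one phrase in seven rows, within a protocol amendment. Analysis, sample size and data collection are unaffected.
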